2.9.4 Durvalumab

Durvalumab is a human immunoglobulin G1 kappa (IgG1 κ) monoclonal antibody that blocks the interaction of programmed cell death ligand 1 (PD-L1) with the PD-1 and CD80. It is composed of 2 identical heavy chains and 2 identical light chains, with an overall molecular weight of approximately 149 kDa. Durvalumab contains a triple mutation in the constant domain of the Ig G1 heavy chain that reduces binding to complement protein C1q and the fragment crystallizable gamma receptors involved in triggering effector function.

It works as a checkpoint inhibitor, blocking a signal that would have prevented activated T cells from attacking the cancer, thus allowing the immune system to clear the cancer.

It is indicated as monotherapy for the treatment of locally advanced, unresectable non-small cell lung cancer (NSCLC) in adults whose tumors express PD-L1 on \geq 1% of tumor cells and whose disease has not progressed following platinum-based chemoradiation therapy.

2.9.5 Overall risks

Monoclonal antibodies directed against immune checkpoint proteins, such as programmed cell death ligand 1 (PD-L1) as well as those directed against programmed cell death-1 (PD-1) or cytotoxic T-lymphocyte antigen-4 (CTLA-4), aim to boost endogenous immune responses directed against tumor cells. By stimulating the immune system however, there is the potential for adverse effects on other tissues.

Most adverse drug reactions seen with the immune checkpoint inhibitor class of agents are thought to be due to the effects of inflammatory cells on specific tissues. These risks are generally events with a potential inflammatory or immune mediated mechanism and which may require more frequent monitoring and/or unique interventions such as immunosuppressants and/or endocrine therapy. These immune mediated effects can occur in nearly any organ system, and are most commonly seen as gastrointestinal AEs such as colitis and diarrhoea, pneumonitis/interstitial lung disease (ILD), hepatic AEs such as hepatitis and liver enzyme elevations, skin events such as rash and dermatitis and endocrinopathies including hypo- and hyper-thyroidism.

2.9.5.1 Durvalumab

Risks with durvalumab include, but are not limited to, diarrhea/colitis pneumonitis/ILD, endocrinopathies (hypo- and hyper-thyroidism, type I diabetes mellitus, hypophysitis and adrenal insufficiency) hepatitis/increases in

transaminases, nephritis/increases in creatinine, pancreatitis/increases in amylase and lipase, rash/pruritus/dermatitis, myocarditis, myositis/polymyositis, other rare or less frequent inflammatory events including neurotoxicities, infusion-related reactions, hypersensitivity reactions, and infections/serious infections.

For information on all identified and potential risks with durvalumab please always refer to the current version of the durvalumab IB.

Further information on these risks can be found in the current version of the durvalumab IB.

In monotherapy clinical studies AEs (all grades) reported very commonly ($\geq 15\%$ of patients) are fatigue, nausea, decreased appetite, dyspnea, cough, constipation, diarrhea, vomiting, back pain, pyrexia, asthenia, anemia, arthralgia, peripheral edema, headache, rash, and pruritus. Approximately 9.4% of patients experienced an AE that resulted in permanent discontinuation of durvalumab and approximately 6.5 % of patients experienced an SAE that was considered to be related to durvalumab by the study investigator.

The majority of treatment-related AEs were manageable with dose delays, symptomatic treatment, and in the case of events suspected to have an immune basis, the use of established treatment guidelines for immune-mediated (Appendix A detailed summary of durvalumab monotherapy AE data can be found in the current version of the durvalumab IB.

2.9.6 Rationale for fixed dosing

A population PK model was developed for durvalumab using monotherapy data from a Phase I study (study 1108; N=292; doses= 0.1 to 10 mg/kg Q2W or 15 mg/kg Q3W; solid tumors). Population PK analysis indicated only minor impact of body weight (WT) on the PK of durvalumab (coefficient of ≤ 0.5). The impact of body WT-based (10 mg/kg Q2W) and fixed dosing (750 mg Q2W) of durvalumab was evaluated by comparing predicted steady state PK concentrations (5th, median and 95th percentiles) using the population PK model. A fixed dose of 750 mg was selected to approximate 10 mg/kg (based on median body WT of ~75 kg). A total of 1000 patients were simulated using body WT distribution of 40–120 kg. Simulation results demonstrate that body WT-based and fixed dosing regimens yield similar median steady state PK concentrations with slightly less overall between-patient variability with fixed dosing regimen.

Similar findings have been reported by others (Ng et al 2006, Wang et al 2009, Zhang et al 2012, Narwal et al 2013) Wang and colleagues investigated 12 monoclonal antibodies and found that fixed and body size-based dosing perform similarly, with fixed dosing being better for 7 of 12 antibodies (Wang et al 2009) . In addition, they investigated 18 therapeutic proteins and peptides and showed that fixed dosing performed better for 12 of 18 in terms of reducing the between-patient variability in pharmacokinetic/pharmacodynamics parameters (Zhang et al 2012).

A fixed dosing approach is preferred by the prescribing community due to ease of use and reduced dosing errors. Given expectation of similar pharmacokinetic exposure and variability, we considered it feasible to switch to fixed dosing regimens. Based on average body WT of 75 kg, a fixed dose of 1500 mg Q4W durvalumab (equivalent to 20 mg/kg Q4W) is included in the current study.

To date durvalumab has been given to more than 8000 patients as part of ongoing studies either as monotherapy or in combination with other anti-cancer agents. Details on the safety profile of durvalumab monotherapy refer to the current durvalumab Investigator's Brochure for a complete summary of non-clinical and clinical information including safety, efficacy and pharmacokinetics

Durvalumab has recently been approved by FDA for the treatment of patients with locally advanced or metastatic urothelial carcinoma who either have disease progression during or following platinum-containing chemotherapy or have disease progression within 12 months of neoadjuvant or adjuvant treatment with platinum-containing chemotherapy

As regards colorectal cancer a monotherapy with CPI have not demonstrated clinically meaningful efficacy in the majority of mCRC, the MSS mCRC cohort, which are cold tumors with a low mutational burden.

However, in the small percentage of MSI mCRC (5%) they are proving outstanding results. In fact, two works were published recently by Overman et al, the first one with Nivolumab (Overman et al) and the second one with Nivolumab and Ipilimumab in combination (Overman et al). These studies showed an ORR of 31% and 55% and a 1y-PFS of 50% and 71%, respectively.

2.10 Durvalumab background/non-clinical and clinical experience

The non-clinical and clinical experience is fully described in the most current version of the durvalumab Investigator's Brochure.

Durvalumab is a human monoclonal antibody (mAb) of the immunoglobulin G (IgG) 1 kappa subclass that inhibits binding of PD-L1 and is being developed by AstraZeneca/MedImmune for use in the treatment of cancer (MedImmune is a wholly owned subsidiary of AstraZeneca; AstraZeneca/MedImmune will be referred to as AstraZeneca throughout this document.). The proposed mechanism of action (MOA) for durvalumab is interference in the interaction of PD-L1 with PD-1 and CD80 (B7.1). Blockade of PD-L1/PD-1 and PD-L1/CD80 interactions releases the inhibition of immune responses, including those that may result in tumor elimination. *In vitro* studies demonstrate that durvalumab antagonizes the inhibitory effect of PD-L1 on primary human T cells resulting in the restored proliferation of IFN- γ (Stewart et al 2015). *In vivo* studies have shown that durvalumab inhibits tumor growth in xenograft models via a T-cell-dependent mechanism (Stewart et al 2015). Based on these data, durvalumab is expected to stimulate the patient's antitumor immune response by binding to PD-L1 and shifting

the balance toward an antitumor response. Durvalumab has been engineered to reduce antibody-dependent cellular cytotoxicity and complement-dependent cytotoxicity.

To date durvalumab has been given to more than 8000 patients as part of ongoing studies either as monotherapy or in combination with other anti-cancer agents. Details on the safety profile of durvalumab monotherapy are summarized in Section 0. Refer to the current durvalumab Investigator's Brochure for a complete summary of non-clinical and clinical information including safety, efficacy and pharmacokinetics.

2.11 Rationale for Regorafenib dose in combination with Durvalumab

Regorafenib will be administered at a dose of 90 mg orally, once daily (q.d.) for 3 weeks in a 4-week cycle. Durvalumab will be administered intravenously (i.v.) at a dose of 1500 mg every 4 weeks (Q4W).

The dose of regorafenib is lower than the dose currently approved in CRC and other indications. The selection of this dose is based on the recently published REGONIVO trial as well as data from other ongoing trials, as explained below. REGONIVO was a phase Ib trial that enrolled 50 patients with pre-treated metastatic gastric and colorectal cancer. Patients received (during the dose expansion phase), 80-120 mg of regorafenib in combination with nivolumab. The 80 mg dose had a manageable safety profile and encouraging antitumor activity (objective tumor response 40%) in patients with heavily pretreated disease. Based on these promising results, the Rego-Nivo combination is being tested in a number of ongoing clinical trials, including an industry-sponsored phase II trial in patients with mismatch repair-proficient advanced colorectal cancer and two phase II trials in unresectable HCC.

Based on data from the combination of regorafenib and nivolumab in the REGONIVO trial, the combination of regorafenib and pembrolizumab in an ongoing HCC trial, as well as ongoing data from a phase II regorafenib + nivolumab trial in colorectal cancer (Bayer - data on file), a few observations are noted:

- A starting dose of 120 mg of regorafenib cannot be sustained in the majority of patients, predominantly due to rash.
- A starting dose of 80 mg is more tolerable and certain patients can maintain therapy at this dose as well as escalate to 120 mg; however approximately 25% of Western patients require further dose reduction.

It is therefore not clear whether additional efficacy beyond that seen with an 80 mg starting dose could be observed, this suggests that the optimal dose of regorafenib in combination with a PD-(L)1 inhibitor may lie between 80 and 120 mg.

Since there is no pharmacodynamic marker for the regorafenib activity in combination with a PD-(L)1 inhibitor, empirically one can conclude that an intermediate dose closer to 80 mg would have a lower likelihood of eliciting toxicity. However, concerns regarding unrealized efficacy may remain. Conversely, a dose closer to 120 mg may elicit toxicity, leading to higher rates of discontinuation.

A further consideration is that some patients treated with 80 mg of regorafenib still require dose reductions and with 40 mg tablets, a 50% dose reduction is drastic and not considered usual practice.

Based on PK and PD data from the phase I dose escalation trial (11650), regorafenib exposure in the range expected for a dose of 40 mg had less of an impact on levels of sVEGFR2 as compared to exposure associated with doses \geq 60 mg. Since VEGFR inhibition is one of the proposed mechanisms for the beneficial effect of regorafenib and PD-(L)1 inhibitor combination therapy, this is relevant to consider.

Dosing regorafenib in combination using a lower strength tablet would allow flexibility to achieve a starting dose between 80 and 120 mg and have a more gradual dose reduction if needed.

In order to provide maximum flexibility to attain an optimal dose, with the current information, 30 mg tablets are optimal. A starting dose of 90 mg (3 tabs) in combination therapy is recommended. Should an initial dose reduction be required, the first dose reduction would be to 60 mg (2 tablets), which is a more conventional 30% reduction and is also expected to provide regorafenib exposure in a pharmacologically active range.

3 STUDY OBJECTIVES

3.1 Primary Objective

The primary objective of this study is:

- To investigate the efficacy of Regorafenib plus Durvalumab versus control arm as adjuvant treatment in stage IV CRC patients rendered Disease-Free after completion of standard treatment according to local practices.

3.1.1 Primary Endpoint

The primary endpoint is Disease-Free Survival (DFS) defined according to Punt, 2007 (Table 4)[60]. In addition to the Punt definition, one the following will be considered DFS event as well :

- a) Appearance of any imaging or clinical new sign of disease
- b) Two consecutive (time gap will be decided by the clinical investigator but it should not be longer than 30 days) increases in CEA levels above upper limit level.

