Feasibility: need for crossover	
Any trial randomizing active treatments vs a no –treatment-control presents feasibility problems. In this setting, where the large majority of patients will relapse within a few months, randomizing to an inactive control vs the possibility of receiving entirely innovative treatments will constitute a prohibitive feasibility obstacle.
 
This may be overcome by offering the most innovative treatment (REGO DURVA) to patients randomized to control whenever they relapse. This will also provide an opportunity for the conduct of a “satellite” phase IIa trial among a patient population that should present very good conditions and with a not too bulky disease load. Because this crossover will not affect the primary endpoint of the study, this part of the study will be addressed and better specified only if the main protocol is approved. As to the amount of Durvalumab to be provided for this part, we may expect that 1/3 of patients will not be eligible for the cross over and we may postulate that among those starting palliative Durvalumab + Regorafenib, patients will receive a median of 4 months of therapy.

Primary Endpoint	
Disease-Free Survival (DFS) will be defined by Punt, JNCI 2007
 
In addition to the Punt definition, the following condition will be considered DFS event: Two consecutive increases in CEA levels above upper limit level (time gap decided by the clinical investigator but no longer than 30 days).

Secondary Endpoints	
 • 18-months Disease-Free Survival (DFS) • Adverse events and Toxicity • Overall Survival (OS) • Compliance to the experimental treatment.
Exploratory Endpoints	
 • Association of translational research data (ctDNA, NGS) with the outcomes

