	
crossover part of the study will be analyzed by means of proportional hazard time-depended analysis. Median disease-free survival will be calculated with the Kaplan-Meier method.
 
All statistical testing is two-sided at the nominal 5% significance level, with no adjustment for multiplicity. All patients who receive at least one regorafenib plus durvalumab dose will be included in the safety analysis.

Publication plan	
 - Timelines 2025 Q4 - Target Journals: Lancet, Lancet Oncology, JCO.

Table 1. SCREENING PHASE

	28 to 1 day before randomization ^d	
Informed consent	X	
Inclusion / Exclusion criteria	X	
General disease medical history	X	
Prior / Concomitant medications	X	
Complete physical examination	X	
ECOG PS	X	
Weight	X	
Vital Signs ^a	X	
12-lead ECG ^b	X	
Tumor imaging ^c	X	Must be performed within 10 weeks before D1C1. Tumor imaging can be accepted even if performed before the procedures to obtain NED status.
Hematology, chemistry, coagulation and pregnancy test ^d	X	
Biomarkers ^d	X	CEA and CA 19-9 must be on normal range
Histologic Confirmation	X	Only if surgery performed to obtain NED state, resection of the metastases must be R0

Table 2. Experimental arm

	From -7 days to Day 1 Cycle 1	Day 1 Cycle 1	Day 8, 15, 22 Cycle 1	Day 1 Cycle 2	Day 15 Cycle 2	Day 1 Cycle 3 and above up to 1-year (12 cycles)	QW12 from C1D1 (+/- 7 days)	End of treatment visit	Treatment discontinuation 30-days from last treatment or at initiation of other anticancer therapy (whichever occurs first)	Follow-up period ^g
Prior / Concomitant medications								X		X
Complete physical examination								X		X
Limited physical examination ^a		X	X	X	X	X				
ECOG PS		X	X	X	X	X		X		X
Weight		X		X		X				
Vital Signs ^a		X	X	X	X	X		X		X
12-lead ECG ^b								X		

Tumor imaging/ response assessments ^c							X	X		X
Hematology ^d	X		X	X	X	X		X		
Coagulation ^d	X							X		
Chemistry ^d	X		X	X	X	X		X		
Biomarkers ^d							X	X		X
Durvalumab Administration		X ^e		X ^e		X ^f				
Regorafenib Administration		X ^e		X ^e		X ^f				
AEs assessments	X		X	X	X	X		X	X	X
Survival and anti-cancer therapy									X	X

Table 3 - Control arm

	QW12 from C1D1 (+/- 7 days)	End of treatment visit	Treatment discontinuation 30-days from last treatment or at initiation of other anticancer therapy (whichever occurs first)	Follow-up period ^g
Prior / Concomitant medications	X	X		X
Complete physical examination	X	X		X
ECOG PS	X	X		X
Weight	X	X		
Vital Signs ^a	X	X		X

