4.3 Study plan

Approximately 182 patients, >18 years of age, with Stage IV CRC and no evidence of disease (NED) will be enrolled. Randomization will be 1:1.

Prior to enrolment, all patients will have received standard of care (SoC) treatment for Stage IV CRC (locoregional), and will have to be NED.

Treatment schedules and safety and efficacy assessments will be the same for all patients, regardless of treatment group.

All patients will undergo assessments (Section 6.2) to confirm compliance with inclusion and exclusion criteria, after that they will sign informed consent. Patients who will be randomized to the experimental treatment group will receive up to 1 year of regorafenib plus durvalumab.

Run-in phase: The combination of an immune-checkpoint inhibitor plus TKI anti-angiogenic agents has been extensively investigated in several trials (phase II and III) in different types of tumors, with no evidence of new safety signals. Although specific data are not available on the combination of durvalumab and regorafenib, we would not expect major toxicity issues.

Therefore, a run-in phase will be conducted on the first 4 patients randomized to the experimental arm using a starting dose of 60 mg/die of Regorafenib (and fixed 1500 mg of Durvalumab), to be escalated after 2 months to 90 mg/die if < 2 patients report serious adverse events (SAE). If Regorafenib 90 mg/die is well tolerated for other 2 months (< 2 patients with SAE) the run-in phase will be closed with the dose of 90 mg/die. In case of > 2 patients report SAE with 90 mg/die, additional 4 patients will be enrolled and treated with the same dose of Regorafenib (90 mg/die) and if < 2 of them report SAE the run-in will be closed at 90 mg/die. Conversely, if > 2 patients report SAE the dose of Regorafenib will be reduced again to 60 mg/die and the run-in will be closed with Regorafenib 60 mg/die.

If during the first part of the run-in > 2 patients report SAE with Regorafenib 60 mg/die, additional 4 patients will be treated with Regorafenib 30 mg/die for 2 months and, in case of > 2 patients with SAE, the trial will be revised. In case of good tolerance of Regorafenib 30 mg/die (< 2 patients with SAE), additional 4 patients will be enrolled and treated with Regorafenib 60 mg/die: if > 2 patients will report SAE the run-in phase will be closed with Regorafenib 30 mg/die, instead if Regorafenib 60 mg/die will be well tolerated (< 2 SAE) this will be the final dose of the run-in phase.

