8.1 Study Visits

8.1.1 Screening

Screening, to verify inclusion and exclusion criteria, will include:

1. obtaining written informed consent from patient or legally authorised representative (Section 8.2.1.1)
2. Review of eligibility criteria
3. documentation of demographics and medical history (Section 8.2.1.2)
4. Complete physical examination (Section 8.2.2.1)
5. vital signs (Section 8.2.2.2)
6. ECOG performance status (Section 8.2.2.3)
7. 12-lead electrocardiogram (ECG; Section 8.2.2.4)
8. clinical chemistry, coagulation profile and haematology (Section 8.2.2.45)
9. CEA and CA 19-9 analysis, backup plasma sample (Section 8.2.3.2)
10. pregnancy test (serum or urine) for female patients of child-bearing potential (Section 8.2.1.3); patients with positive results will be discontinued from the study with no further study procedures performed
11. CT/MRI/PET scan of chest and abdomen with tumor measurement and evaluation by RECIST 1.1 criteria (Section 8.2.3.3)
12. documentation of prior and concomitant medications (Section 7.7)
13. Histological confirmation

Patients who meet the inclusion/exclusion criteria (Section 6) will be randomized to one of the following:

1. Treatment arm (Regorafenib + Durvalumab)
2. Control arm

8.1.2 Treatment Phase: Table 2 and 3.

Patients allocated to regorafenib + durvalumab arm will undergo visits every week for the first cycle, every 2 weeks for the second cycle, and monthly thereafter.

Patients allocated to the control group will undergo visits every 12 weeks.

If at any time a relapse is confirmed, the patient will discontinue treatment. Patients in the control arm will be offered to crossover to regorafenib plus durvalumab.

All visits have a window of ± 7 days.

- Patients allocated to Treatment arms will undergo the following procedures and assessments:

At each visit:

1. Limited physical examination
 2. vital signs
 3. ECOG performance status
 4. Weight
 5. Clinical chemistry and haematology (CBC + differential platelet count; creatinine; total bilirubin; AST; ALT; alkaline phosphatase; LDH; albumin; glucose; potassium; sodium; calcium)
 6. administration of therapy (regorafenib plus durvalumab at Day 1 of every cycle)
 7. documentation of AEs/SAEs
 8. documentation of concomitant medications and procedures (at Day 1 of every cycle)
 9. CEA and CA19-9 analysis and CT/MRI/PET scan as per baseline assessment: every 12 weeks. From day 1 (\pm 7 days).

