- Patients allocated to no further treatment (Control Group) will undergo the following procedures and assessments:
at each visit (every 12 weeks.)
 1. physical examination
 2. vital signs
 3. ECOG performance status
 4. Weight
 5. pregnancy test (serum or urine) for female patients of child-bearing potential
 6. Clinical chemistry and haematology (CBC + differential platelet count; creatinine; total bilirubin; AST; ALT; alkaline phosphatase; LDH; albumin; glucose; potassium; sodium; calcium)
 7. documentation of AEs/SAEs
 8. documentation of concomitant medications and procedures
 9. CEA and CA 19-9 analysis
 10. CT/MRI/PET scan as per baseline assessment

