8.2.3 Efficacy Assessments

8.2.3.1 Relapse

Any of the following events will be considered as relapse: loco-regional recurrence (as defined in Section 3.3.1), distant metastases, death from same cancer or death from other cancer, non-cancer-related death, and treatment-related death.

A positive CT/MRI/PET scan (appearance of a lesion) will be considered evidence of relapse. Two consecutive increases in CEA levels above upper limit level (time gap decided by the clinical investigator).

Confirmation of progression guidelines are set for the following reasons:

- for patient management and treatment decisions
- in the absence of significant clinical deterioration, to promote the collection of additional scans after the first radiologic RECIST 1.1 assessment of progressive disease (PD) in order to distinguish pseudoprogression from true radiologic progression, also known as RECIST 1.1 modified for confirmation of progression
- when scans are evaluated by Investigator and by BICR, to reduce informative censoring by Investigator assessments (Investigator assesses PD at a time-point earlier than does BICR).

Confirmed objective disease progression refers to either of the following scenarios: 1. clinical progression/deterioration followed by a radiologic verification scan (PD by RECIST 1.1); or 2. in the absence of significant clinical deterioration, radiologic PD by RECIST 1.1 followed by a second radiologic confirmation scan with PD assessed according to the specific confirmation of progression criteria listed below. RECIST 1.1 modified for confirmation of progression refers to the second scenario above. The confirmatory scan should occur preferably at the next scheduled imaging visit and no earlier than 4 weeks following the date of the immediate prior assessment of RECIST 1.1 PD.

Immediate prior radiologic progression would be considered confirmed if any the following criteria are met in the confirmatory scan:

- $\geq 20\%$ increase in the sum diameters of target lesions (TLs) compared with the nadir at 2 consecutive visits, with an absolute increase of at least 5 mm in sum of diameters compared to nadir,
- and/or significant progression (worsening) of non-target lesions (NTLs) and/or of pre-existing new lesions at the confirmatory scan time-point

compared with the immediate prior time-point (Note: Pre-existing new lesions are evaluated as NTLs at the confirmatory scan time-point),

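### The CEA component of DFS needs two raised values within 30 days, which routine 12-weekly testing cannot supply, and Section 8.2.3.1 states the rule without that limit

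*Combined protocol and SAP*

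**What the plan says.** Section 3.1.1 adds to the published DFS definition an event (b): two consecutive CEA increases above the upper limit, where the "time gap will be decided by the clinical investigator but it should not be longer than 30 days". The Synopsis has the same limit: "time gap decided by the clinical investigator but no longer than 30 days". Section 8.2.3.1 gives the rule again, as "Two consecutive increases in CEA levels above upper limit level (time gap decided by the clinical investigator", and there the parenthesis closes with no limit of 30 days.

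The testing schedule is in Section 8.1.2 and Tables 2 and 3. For the experimental arm Section 8.1.2 has "CEA and CA19-9 analysis and CT/MRI/PET scan as per baseline assessment: every 12 weeks". For controls, "Patients allocated to the control group will undergo visits every 12 weeks", and CEA is on the list of procedures "at each visit (every 12 weeks". Both tables mark biomarkers under a column headed "QW12 from C1D1 (+/- 7 days", at an end-of-treatment visit, and in follow-up. Follow-up visits in months 13-24 are 3-monthly in Section 8.1.4 and 4-monthly in table footnote g. After that they are every 4-6 months or every 6 months respectively.

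Sections 8 and 8.2.3.2 ask for CEA results obtained as standard of care to be entered in the eCRF, but no section requires a repeat after a raised value. The trial is open label (Section 4.1.2). Section 4.3 says: "Treatment schedules and safety and efficacy assessments will be the same for all patients, regardless of treatment group".

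**The concern.** A component of the primary endpoint should be ascertainable from the visits the protocol schedules, in the same way in both arms. Here the interval in the definition and the interval in the schedule do not meet, and two sections give different rules for the same event.

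What remains is a retest at the discretion of someone who knows the allocation. Experimental patients attend weekly, then 2-weekly, then monthly, with blood drawn; controls attend every 12 weeks. An extra CEA is therefore easier to obtain in the experimental arm. The incentive points the other way: a declared relapse opens crossover for a control patient (Sections 3.1.2 and 4.1), whereas a confirmed relapse ends treatment for an experimental patient (Section 8.1.2). Unequal retesting would date relapse earlier in one arm without any treatment effect. The planned sensitivity analyses, restricted mean survival time (Section 4.2) and a covariate-adjusted Cox model (Section 5.2.6), keep CEA-only events in and would not show it.

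**Working it through.** **The plan's own figure.** Schoenfeld's formula for a hazard ratio of 0.60, two-sided 0.05 and 90% power gives 4 × (1.960 + 1.282)² / (ln 0.60)² ≈ 161.1, rounded up to 162 events, against the stated 164. Inflating 172 for 5% attrition gives 172/0.95 = 181.05, rounded up to 182. The sample size reproduces and is not affected by this point.

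**Smallest gap between consecutive routine CEA tests** (nominal gap minus a 7-day window at each end; the Section 8.1.2 window is assumed to apply in follow-up):

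| Interval | Nominal days | Smallest gap |
|---|---|---|
| 12 weeks | 84 | 84 − 14 = 70 |
| 3 months | 91 | 77 |
| 4 months | 122 | 108 |
| 6 months | 183 | 169 |

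All exceed 30 days. Screening cannot supply the first raised value, because inclusion criterion 10 requires a normal CEA.

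**The end-of-treatment test.** Section 8.1.3 defines this visit as the last planned dosing visit, here Cycle 12 Day 1: 1 + 11 × 28 = day 309. Week 48 is 1 + 48 × 7 = day 337. The nominal gap is 28 days, or 14 to 42 with both windows, so this pair may qualify. For early discontinuation the visit is the one at which stopping is decided, which can also fall within 30 days of a 12-weekly test. Table 3 marks the visit for controls too, but Section 8.1.3 defines it only through dosing, and its list of assessments omits CEA.

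**Same patient, two rules.** Take a patient with negative scans and raised CEA at weeks 12 and 24 (84 days apart), with no other test.
- Section 3.1.1 and Synopsis: 84 > 30, no event.
- Section 8.2.3.1: event.
- If the investigator repeats the test 28 days after week 12 and it is again raised, it is an event under both, and 84 − 28 = 56 days before the week-24 scan.

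**Possible size, by simulation with no true effect.** From the documents: 91 per arm, median 6 months (applied to both arms), 2 years of accrual plus 2 of follow-up (censoring uniform over 24-48 months). Assumed: exponential relapse times, detection at the next 12-weekly scan, a fraction f of relapses with raised CEA one visit before the positive scan, and a repeat that dates the event 28 days after that visit. With 800 trials per setting:

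| f | Retested: control / experimental | Apparent HR | Two-sided rejection |
|---|---|---|---|
| 20% | 100% / 100% | 0.99 | 4.4% |
| 20% | 100% / 50% | 0.98 | 5.6% |
| 20% | 100% / 0% | 0.96 | 5.0% |
| 40% | 100% / 100% | 0.99 | 4.6% |
| 40% | 100% / 50% | 0.95 | 5.6% |
| 40% | 100% / 0% | 0.92 | 7.9% |

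The simulation error on a rejection rate is about √(0.05 × 0.95/800) = 0.8 percentage points.

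Thinning the scans to 16-weekly after week 48 gives, for 100% versus 50%, a hazard ratio of about 0.95-0.97, or 1.03-1.06 with the arms reversed. Across all runs the spread was 0.94-0.99 and 1.01-1.06. Rejection was 4.6-5.8%, or 5.4-6.6% reversed. For all-versus-none, hazard ratios ran from 0.87 to 0.96 and rejection from about 5% to 9%.

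**The case against.** The strongest reply is that Section 3.1.1 leaves the investigator the gap, not the choice of whether to retest. Read as a confirmation rule (a raised scheduled value, then a repeat within 30 days), it makes sense and only the schedule lacks the line. That reading is open, and standard-of-care values are already collected. But nothing in the schedule makes the repeat obligatory, and this reading does not explain why Section 8.2.3.1 drops the limit.

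Second, imaging is scheduled together with CEA in both arms, and event (a) counts any new imaging or clinical sign. Most patients with a CEA-only event would be events anyway, so mainly timing moves. This stands, and it is why the shift is small beside the design hazard ratio of 0.60.

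A reader might infer more than the documents support:
- *No scheduled pair can ever qualify, or only the experimental arm has one.* Both tables mark an end-of-treatment CEA, and it can fall within 30 days of a 12-weekly test. What it means for controls is unclear, so no firm arm difference can be drawn from it.
- *Two 12-weekly values never count.* That is true under Section 3.1.1 and the Synopsis but not under Section 8.2.3.1.
- *The bias favours the experimental arm, with a false-positive rate of 8-9%.* That needs every eligible control and no experimental patient to be retested, although experimental patients are seen more often. Opportunity and incentive pull in opposite directions, and the documents do not settle which prevails.

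**Conclusion.** The defect is real and should be fixed. The capped CEA event cannot arise from routine 12-weekly or follow-up tests. It rests almost entirely on off-schedule retesting by unblinded investigators, and two sections assign different event status to the same patient.

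The direction of any bias is open and its size is not in the documents. It is modest under 100% versus 50% retesting, where type I error stays near nominal, and material only in the all-versus-none extreme. These sizes rest on the assumed CEA-lead fraction of 20-40%, the assumed retesting rates and exponential relapse. The interval arithmetic and the conflict between Sections 3.1.1 and 8.2.3.1 need none of those assumptions.

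**What to change.** 1. Reconcile the Synopsis, Section 3.1.1 and Section 8.2.3.1 to one CEA rule.
2. State in Sections 3.1.1, 8.1.2 and 8.2.3.1 and in Tables 2 and 3 that any CEA above the upper limit triggers one repeat, in a fixed window of at most 30 days, identically in both arms and recorded in the eCRF. Remove the investigator's choice of gap.
3. Define the date of a CEA event, and say how standard-of-care values outside the mandated pair are handled.
4. Clarify the end-of-treatment CEA: whether Section 8.1.3 includes it, and what that visit means for controls in Table 3.
5. Add a sensitivity analysis of DFS that excludes CEA-only events, and report the number of repeats by arm.

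The cost is protocol wording and one extra local blood draw for patients with a raised value. Because a declared relapse stops treatment or opens crossover, a mandated repeat will also bring some of those decisions forward; the sponsor should acknowledge this. The sample size does not change.
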